Given the serious personal consequences associated with trichotillomania and skin picking disorder, and the likelihood of success of dronabinol in treating both disorders, the aim of the present study was to examine the efficacy and safety of dronabinol vs placebo in adults with trichotillomania or skin picking disorder using a double-blind, placebo-controlled design.

We hypothesize that dronabinol will be more effective than placebo in reducing the frequency of hair pulling and skin picking and in improving overall psychosocial functioning after 10 weeks of treatment when compared to baseline.

Primary Aim/Objective

The aim of the present study is to examine the efficacy and safety of dronabinol vs placebo in adults with trichotillomania and skin picking disorder.

Co-Primary Endpoint(s):

The co-primary efficacy measures will be the change in hair pulling or skin picking frequency and urges to pull hair or pick skin for the past week as indicated by change in total score on the *NIMH Trichotillomania Symptom Severity Scale* (for TTM) or *Skin Picking Symptom Assessment Scale* (for SPD), reliable and valid clinician-administered measures (18-19), as well as the same scale modified for skin picking disorder, and the change in psychosocial functioning over the same time period using the *Sheehan Disability Scale* (20). The co-primary efficacy end points will be the change in these measures from baseline to week 10.

Secondary Aim/Objective

A secondary aim of the study is to examine the effects of dronabinol vs placebo on self-report measures of hair pulling, skin picking, quality of life, and measures of mood and anxiety.

Secondary Endpoint(s):

Secondary efficacy measures include the change in number of days per week pulling, the *Clinical Global Impressions–Improvement Scale* (CGI-I) rated global improvement of symptoms over time (results will be dichotomized as improved [CGI-I ratings of 1 or 2 very much/much improved] or not improved [CGI-I ratings of 3-7]) (20), the self-report *Massachusetts General Hospital Hairpulling Scale* (22), the *Skin Picking Symptom Assessment Scale*, the *Quality of Life Inventory* (23), the *Hamilton Depression Rating Scale* (24), the *Hamilton Anxiety Rating Scale* (25), and the *Tridimensional Personality Questionnaire*

Methodology

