- 8) Cognitive impairment that interferes with the capacity to understand and self-administer medication or provide written informed consent

Baseline Assessments:

Those subjects who appear appropriate for the study, based on telephone screening, will be invited for a baseline assessment. The duration of the baseline assessment will be approximately 90 minutes and will include the following: informed consent, demographic data, concomitant medications (no psychotropic medications will be allowed), and family history data. There will also be a physical examination (including weight, and vital signs, urine pregnancy test for women of childbearing years and urine drug screen, as well as a baseline blood draw to assess nutritional status. The blood draw is optional to the subject and will administered at the PI's discretion). Finally, the subjects will undergo a psychiatric evaluation (using the MINI International Neuropsychiatric Interview).

In addition, the following instruments will be completed at the screening visit: 1) NIMH Trichotillomania Symptom Severity Scale (or the same scale modified for skin picking); 2) Sheehan Disability Scale; 3) Massachusetts General Hospital Hairpulling Scale; 4) the 17-item

Hamilton Rating Scale for Depression (HAM-D); 5) the 17-item Hamilton Rating Scale for Anxiety (HAM-A); 6) Clinical Global Impression (Improvement and Severity) scale; 7) Cambridge Caffeine Use Questionnaire; 8) The Dietary Fat and Free Sugar Questionnaire and 9) the Quality of Life Inventory; 10) Cambridge-Chicago Trait Scale (12); the Skin Picking Symptom Assessment Scale (SP-SAS); and the Body Focused Repetitive Behavior Broad Assessment Measure (BFRB-BAM), a new scale being added for validation purposes. In addition, subjects will undergo cognitive assessments at baseline and study endpoint.

Cognitive Assessments: Assessments of cognitive control will be comprised of several valid paradigms (See below). These tasks are designed to probe dissociable neural circuitry and cognitive processes likely to be implicated in the pathophysiology of addictions. Task order was chosen arbitrarily and will be applied consistently across subjects, to minimize possible confounding factors of differences in task order across participants.

The following tasks will be administered at baseline and final visits:

- Stop Signal Task of Inhibitory Control (SST)
- Intra-dimensional/Extra-dimensional Set Shift Task (ID/ED task)
- One Touch Stockings Task (OTS)

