- Any moderate adverse event which appears definitely, probably, or possibly related to study participation will be reported to the University of Chicago IRB in writing within 20 working days.
- Any mild adverse event will be summarized in the IRB annual progress reports.

Statistical Analysis

Design/Randomization

The study is a double-blind, placebo-controlled study. Participants will be randomized (1:1) to receive dronabinol or placebo by the University of Chicago Investigational pharmacy in block sizes of eight, using computer-generated randomization with no clinical information.

Due to the pandemic of COVID19, study participants can perform their baseline and follow-up visits online using encrypted Zoom instead of in person visits. All inventories will be assessed. Blood samples and urine toxicology, however, will be at the discretion of the study PI. In cases where they are considered medically necessary, the participant can have them drawn locally and submitted to the study team.

Efficacy Analysis

For statistical analysis, the full-analysis set will be defined as all participants who took at least 1 dose of the study drug and had at least 1 post-randomization primary efficacy assessment. The safety-analysis set will be defined as all randomized participants who took at least 1 dose of the study drug and completed at least 1 post-randomization safety assessment. Participants with trichotillomania and skin picking disorder will be grouped as one BFRB group.

We will compare the baseline characteristics of both groups using Fisher's exact test for categorical variables and the t test for continuous variables. We will calculate adherence to treatment, based on the number of pills returned at each visit, as the number of pills taken divided by the number of days in the study $\times 100\%$.

Primary endpoint analysis

The primary outcome measure will be the change from first randomization visit to study endpoint in total composite score on the NIMH Trichotillomania Symptom Severity Scale(s) and the Sheehan Disability Scale.

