The primary analysis of efficacy for continuous measures will be analysis of variance (ANOVA), with terms for treatment to assess differences between treatment groups in the change from first randomization visit to endpoint using the last observation carried forward. The primary analysis for global improvement and response categories will be the Cochran-Mantel-Haenszel test using the last observation carried forward. The primary analysis for $\geq 5\%$ reduction in weight will be Fisher's exact test using the last observation carried forward.

Secondary endpoints analyses

Secondary outcome measures will include the change from first randomization visit to study endpoint in CGI severity and improvement scales, self-reported hair pulling behavior using the MGH-HPS, self-reported skin picking behavior using the SP-SAS, the change in depressive and anxiety symptoms, change in quality of life, and impacts on personality markers. We will use a longitudinal analysis comparing the rate of change of the outcome during the treatment period between groups. The difference in rate of change will be estimated by random regression methods. The model for the mean of the outcome will include terms for treatment, time, and treatment-by-time interaction. To account for the correlation of observations within participants, we will use SAS procedure MIXED with a first-order antedependence covariance structure. The longitudinal analyses will use all available observations from all time points from all participants who completed a randomization visit evaluation.

Safety analyses

We will evaluate differences between groups in the incidence of treatment-emergent adverse events using Fisher's exact test. Descriptive statistics will be used to evaluate changes in laboratory values, blood pressure and heart rate.

Sample Size

The sample size was calculated for the co-primary endpoint of change from randomization. For 80% power to compare the change from randomization, assuming a true effect size of 0.5 between treatment group and the placebo group, 50 participants with a BFRB will be needed in each treatment group based on a 2-group t test at the .05 level of significance. Given the low rates of adverse events expected with dronabinol, we expect few drop-outs from the study and therefore a smaller sample is needed.

Data Management Plan

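### The primary ANOVA of change does not use baseline as a covariate and handles missing data by LOCF alone, so precision may be lost and an earlier score can stand in for week 10

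*Combined protocol and SAP*

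**What the plan says.** All references are to the combined protocol and SAP.

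- **Model.** Primary endpoint analysis: "analysis of variance (ANOVA), with terms for treatment to assess differences between treatment groups in the change from first randomization visit to endpoint". No covariate or stratum is named.
- **Missing data.** The same sentence adds "using the last observation carried forward". No sensitivity analysis of the primary comparison is named.
- **Endpoint.** Co-Primary Endpoint(s): "The co-primary efficacy end points will be the change in these measures from baseline to week 10".
- **Analysis set.** Efficacy Analysis admits participants who "took at least 1 dose of the study drug and had at least 1 post-randomization primary efficacy assessment".
- **Visits.** Methodology implies follow-up at weeks 2, 4, 7 and 10. Following-Up Visit Assessments puts all psychiatric measures except the MINI at each of them.
- **Baseline data.** Baseline Assessments lists the "NIMH Trichotillomania Symptom Severity Scale (or the same scale modified for skin picking") and the Sheehan Disability Scale, among others.
- **Withdrawals.** Subject Withdrawal provides an early-termination visit with the screening instruments, held when the participant can attend.
- **The other model.** Secondary endpoints analyses describes a mixed model and says "The longitudinal analyses will use all available observations from all time points from all participants who completed a randomization visit evaluation". It compares rates of change and is assigned to secondary outcomes.
- **Diagnosis.** Efficacy Analysis: "Participants with trichotillomania and skin picking disorder will be grouped as one BFRB group". Design/Randomization describes "computer-generated randomization with no clinical information".

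**The concern.** There are two separate issues.

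**Precision.** Subtracting baseline is not the same as adjusting for it. A change score fixes the baseline slope at 1; a covariate lets the data estimate it, which usually leaves less residual variance and deals better with chance baseline imbalance. With 50 participants in all there is little precision to spare, and the scores are already collected.

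**What LOCF estimates.** A participant who leaves early can have a week-2, week-4 or week-7 score analysed as the endpoint. Because the daily dose may step up after weeks 2 and 4, an early score also reflects an earlier dose step. With drop-out, the primary estimate becomes a mixture over visits instead of the week-10 change that the protocol defines, and no named analysis of the primary comparison would show whether that matters.

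**Working it through.** **1. The plan's own figure.** Sample Size gives 50 per group for 80% power at effect size 0.5, level .05, without stating sidedness. With n per arm = 2(z_α + z_β)²/d²:
- one-sided: 2(1.645 + 0.842)²/0.25 = 49.5, so 50;
- two-sided: 2(1.960 + 0.842)²/0.25 = 62.8, so 63.

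The stated 50 therefore reproduces only one-sided. Two-sided testing below is my assumption. The planned total is 50 at 1:1, that is 25 per arm. At d = 0.5 the noncentral t gives 41.0% power two-sided (53.9% one-sided). The gap between 50 per group and 50 in total is a separate matter.

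**2. Baseline as a covariate.** The documents give no SDs or correlations, so these are assumed. Let r be the baseline-to-week-10 correlation and k the week-10 SD divided by the baseline SD.

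Variance ratio (ANCOVA / change score) = k²(1 − r²)/(1 + k² − 2rk), which is (1 + r)/2 when k = 1.

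Power uses the noncentral t with effect 0.5/√ratio, 25 per arm, 47 df, two-sided .05 and no drop-out:

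| k | | r = 0.3 | r = 0.5 | r = 0.7 | r = 0.8 |
|---|---|---|---|---|---|
| 1.0 | ratio | 0.650 | 0.750 | 0.850 | 0.900 |
| | power | 57.4% | 51.6% | 46.7% | 44.7% |
| 1.2 | ratio | 0.762 | 0.871 | 0.966 | 0.997 |
| | power | 51.0% | 45.8% | 42.1% | 41.1% |
| 0.8 | ratio | 0.502 | 0.571 | 0.628 | 0.640 |
| | power | 68.6% | 63.0% | 58.9% | 58.1% |

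The gain vanishes where r = 1/k (r = 0.83 at k = 1.2). The formula ignores chance baseline imbalance. Simulation with k = 1 (40,000 trials per r) gave 50.5% at r = 0.5 and 46.2% at r = 0.7, so the tabled powers are up to about 1 point high.

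**3. LOCF, drop-out unrelated to outcome.** Let p be the drop-out proportion in each arm and f the share of the benefit present at the carried visit. The expected difference is 0.50 × [1 − p(1 − f)]. For f from 0 to 1:
- p = 5%: 0.475 to 0.50;
- p = 10%: 0.45 to 0.50;
- p = 20%: 0.40 to 0.50; for example, at f = 0.3, 0.50 × (1 − 0.14) = 0.43.

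Unequal drop-out can create a difference where there is none. Suppose both arms improve linearly by 0.5 SD and 30% v 10% are last seen at week 2. The arm means become 0.5 × (0.70 + 0.30 × 0.2) = 0.38 and 0.5 × (0.90 + 0.10 × 0.2) = 0.46, a gap of 0.08 SD against the arm with more drop-out.

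**4. LOCF, drop-out related to outcome (simulated).** Assumptions: true difference 0.50; r = 0.5 between all visits; equal SDs; drug effect 0.1/0.2/0.4/0.5 SD and placebo improvement 0.2/0.35/0.45/0.5 SD at weeks 2/4/7/10; 3,000 trials per scenario; no early-termination score. In the first three rows the least improved at week 4 leave then.

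| Drop-out | Baseline-adjusted LOCF | Week-10 ANCOVA | Repeated measures |
|---|---|---|---|
| 10% per arm | 0.46 | 0.49 | 0.49 |
| 30% drug, 10% placebo | 0.31 | 0.58 | 0.51 |
| 10% drug, 30% placebo | 0.58 | 0.43 | 0.50 |
| 10% per arm; drug leavers have poor unseen week-10 scores | 0.55 | 0.63 | 0.61 |

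With 10% drop-out per arm unrelated to outcome, last seen at week 2 or 4, power is 46/47/48%. In the last scenario, with no drug effect, type I error is 6.4/8.1/7.6%.

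**5. A diagnosis term.** If 25 of 50 have trichotillomania (assumed), arms of 25 split 15 v 10 or worse in 26% of randomizations (hypergeometric). If diagnosis is unrelated to outcome, a main effect costs about 0.9 point of power. Adding a diagnosis-specific baseline slope brings the cost to about 1.7 points (50.5% to 48.8% at r = 0.5; 46.2% to 44.5% at r = 0.7).

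**The case against.** **The planned test is valid.** This stands. A reader might infer that the ANOVA is biased or that baseline is thrown away. Neither follows: allocation is randomized and the outcome subtracts baseline. The loss is one of precision.

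**Few drop-outs are expected.** Sample Size says so but gives no rate. With none, the LOCF problem disappears and only the covariate point remains. The 30% v 10% scenarios show direction and are not forecasts.

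**The early-termination visit supplies a later score.** It reduces the problem, as may the remote visits allowed under Design/Randomization. It does not remove it: attendance depends on the participant, the score is still not a week-10 value, and no rule says which visit it counts for.

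**A non-LOCF analysis already exists.** In part. Co-Primary Endpoint(s) names the Skin Picking Symptom Assessment Scale for skin picking disorder, and Secondary endpoints analyses puts the same scale under the mixed model. So it would be too strong to say that no co-primary scale has an all-available-data analysis. But that model is not named as a check on the primary comparison, and it targets rates of change.

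**The replacement can do worse.** True when poor responders on drug leave unseen (0.61 against 0.55 for LOCF), hence the missing-not-at-random analysis.

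**A large model is heavy for a 50-person pilot.** Fair. A diagnosis-specific slope has no shown benefit and is not asked for.

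**Conclusion.** The point holds as a recommended change; the trial remains interpretable without it.

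Adding baseline raises power from 41% to roughly 45–57% under equal SDs and r from 0.3 to 0.8, with a wider range (about 41% to 69%) if the SD ratio may lie between 0.8 and 1.2. These figures rest on two-sided testing, 25 per arm, d = 0.5 and no drop-out. It would be tempting to say that adjustment rescues the sample size; at no value examined does it reach 80%.

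The LOCF rule permits a departure from the week-10 endpoint, but the documents do not support saying that the result will be biased, or which way. LOCF understated the effect in some scenarios and overstated it in others. Nor do they show that diagnosis must be in the model: it is not balanced by design, but no power gain is shown.

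**What to change.** Before unblinding, amend the Primary endpoint analysis section as follows.

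1. For each co-primary measure, analyse change at weeks 2, 4, 7 and 10 in a repeated-measures model with treatment, visit, treatment-by-visit, the baseline score of that measure and baseline-by-visit, with the covariance structure named. An unstructured covariance was used in the simulations above, with no convergence failures.
2. Make the week-10 treatment difference the primary contrast. If the model does not converge, use a week-10 ANCOVA with baseline.
3. Name two sensitivity analyses: baseline-adjusted LOCF, and one missing-not-at-random analysis, for example worsening the imputed week-10 scores of dronabinol drop-outs in steps until the conclusion changes.
4. State which visit an early-termination score counts for, and whether the test is one- or two-sided.
5. Reconcile Co-Primary Endpoint(s), Primary endpoint analysis and Secondary endpoints analyses on the severity scale for skin picking disorder. Until then the baseline covariate for that measure is not fully defined. Covariates do not put two different scales on a common metric.
6. Treat a diagnosis main effect as optional.

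**Cost.** SAP wording and a little more analysis; no new data or visits. The model relies on missing-at-random, can overstate benefit more than LOCF if poor responders on drug leave unseen, and can have less power than baseline-adjusted LOCF if benefit is complete early and drop-out is substantial.

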**A Double-Blind, Placebo-Controlled Study of Dronabinol in Trichotillomania and Other
Body focused Repetitive Behaviors**

IRB: 18-0542
Version: 06 June 2020

[name], J.D., M.D., M.P.H.
University of Chicago
Chicago, IL

A Double-Blind, Placebo-Controlled Study of Dronabinol in Trichotillomania

This clinical trial will be conducted in the spirit of Good Clinical Practice (GCP) and in accordance with this IRB approved protocol. No deviation from the protocol will be implemented without the prior review and approval of the IRB except where it may be necessary to eliminate an immediate hazard to a research subject. In such a case, the deviation will be reported to the IRB as soon as possible.

Investigational Agent and Dosing

Dronabinol 5mg to 15mg po qday

Population

The population to be studied for this trial is 50 men and women ages 18-65 who have a current DSM-5 diagnosis of trichotillomania or other body focused repetitive behavior (BFRB) (e.g., skin picking disorder).

Project Goals

The goal of the proposed study is to evaluate the efficacy and safety of dronabinol in trichotillomania. 50 subjects with DSM-5 trichotillomania or other BFRB will receive 10 weeks of double-blind dronabinol or placebo. The hypothesis to be tested is that dronabinol will be effective and well tolerated in patients with trichotillomania or other BFRBs compared to placebo. The proposed study will provide needed data on the treatment of disabling disorders that currently lacks a clearly effective treatment.

Background

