- Rapid Visual Processing Task (RVP)
- Spatial Working Memory Task (SWM)
- Cambridge Gambling Task (CGT)

Following-Up Visit Assessments

All follow-up visits will include all psychiatric measures (except the MINI which will be done at baseline only) and safety measures (adverse events, vital signs, C-SSRS). There will be four follow up visits for a total of five visits.

Subject Compensation

Subjects will be compensated \$20 per visit, for a total of \$100. Compensation will be given in the form of a check at the end of the study, as per University of Chicago protocol.

Safety Assessments

Safety and tolerability will be assessed using spontaneously reported adverse events data, Columbia–Suicide Severity Rating Scale (C-SSRS), vital signs, and by evaluating premature termination. Safety assessments (C-SSRS, sitting blood pressure, heart rate, adverse effects, and concomitant medications) will be documented at each visit. Subjects who are an immediate suicide risk will be removed from the study and appropriate clinical intervention (e.g. hospitalization) will be arranged. Urine pregnancy tests will be performed at the initial visit. Subjects who have a positive urine pregnancy test will be excluded from the study. Assessment of side effects will be done at each visit. AEs will be coded by system organ class (SOC) and preferred term (PT) using the Medical Dictionary for Regulatory Activities (Med- DRA) Version 11.1. The incidences of all AEs will be summarized descriptively. In terms of vital signs, those subjects with abnormal blood pressures will be assessed for symptoms of hypo- or hypertension. Asymptomatic subjects will be evaluated each visit for changes in vital signs. In the case of hypertensive emergencies (BP greater than 210/120), appropriate referral to the emergency room will be made. In the case of hypotension (BP less than 90/60), participants will be evaluated for symptoms of hypotension and if symptomatic, appropriate interventions will be made.

Seizure and seizure-like activity have been reported in patients receiving dronabinol. Therefore, history of seizures will be an exclusion criterion. If a seizure occurs, dronabinol will be discontinued. Participants will be advised to discontinue dronabinol and contact a healthcare provider immediately if they experience a seizure.

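### The carried-forward CGI-I responder analysis can count a stop for intolerance as improved, and neither a sensitivity analysis nor a by-arm summary of premature termination would show how much this matters

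*Combined protocol and SAP*

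**What the plan says.** Under Secondary Endpoint(s), CGI-I is described as "rated global improvement of symptoms over time", and "results will be dichotomized as improved [CGI-I ratings of 1 or 2 very much/much improved] or not improved [CGI-I ratings of 3-7". Nothing there makes response depend on remaining on treatment.

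Under Primary endpoint analysis: "The primary analysis for global improvement and response categories will be the Cochran-Mantel-Haenszel test using the last observation carried forward". No alternative handling of stops and no sensitivity analysis is given. Secondary endpoints analyses also places CGI improvement in a longitudinal mixed model that uses all available observations.

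Subject Withdrawal has withdrawn participants repeat the screening instruments when they can attend an early termination visit. Baseline Assessments lists CGI Improvement and Severity among those instruments.

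Safety Assessments says tolerability is judged partly from "Columbia–Suicide Severity Rating Scale (C-SSRS), vital signs, and by evaluating premature termination". Safety analyses then names two things only: "We will evaluate differences between groups in the incidence of treatment-emergent adverse events using Fisher's exact test" and "Descriptive statistics will be used to evaluate changes in laboratory values, blood pressure and heart rate". Premature termination is not mentioned there.

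Project Goals states the hypothesis: "The hypothesis to be tested is that dronabinol will be effective and well tolerated in patients with trichotillomania or other BFRBs compared to placebo".

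**The concern.** The hypothesis has two parts, efficacy and tolerability. A participant who improves early and then cannot tolerate the drug bears on both. Under the carried-forward rule that participant can enter the responder count as improved at endpoint, although treatment ended before week 10. The by-arm listing of stops and reasons that would tell a reader how many responders are of this kind is not planned. If such cases are more frequent on dronabinol, the responder comparison looks better than it would if response meant improved and still on treatment, and the report would give no means of seeing it.

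**Working it through.** **1. What happens to one such participant under the plan as written**

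| Planned analysis | How an intolerance stop with last CGI-I of 1 or 2 enters |
|---|---|
| CGI-I response, Cochran-Mantel-Haenszel (CMH) test, last observation carried forward | Improved |
| CGI improvement, mixed model | Ratings up to the stop are used; the stop has no role |
| Treatment-emergent adverse events, Fisher's exact test | The event counts, the same as an event that did not end treatment |
| Laboratory values, blood pressure, heart rate | Described; the stop has no role |
| Premature termination | Declared under Safety Assessments; no rate, table, test or reason summary |

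Two other routes exist. The early termination visit may give a rating of 3 to 7, in which case the participant is not improved. A participant who stops before any post-randomization primary efficacy assessment is outside the full-analysis set and counts neither way. So the misclassification is possible, not certain.

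**2. Inputs for size**

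- Arm size: 50 participants in total at 1:1 (Methodology), so 50/2 = 25 per arm. Sample Size speaks of 50 per group but then accepts a smaller number; 25 is used here.
- Dronabinol response: the only rate in the documents is 9/14 = 64.3%, open label (Background). 16/25 = 64% is close to it.
- Placebo response and number of intolerance stops: not in the documents. Both are assumed below.
- The plan states no responder figure, so there is none to reproduce.

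**3. Effect of one recode**

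1/25 = 4 percentage points on that arm's rate.

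**4. Effect on the test**

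Single-stratum CMH chi-square, no continuity correction, n = 25 per arm, N = 50. With a and b improved on dronabinol and placebo and m = a + b:

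expected E = m/2; variance V = n·n·m·(N − m) / [N²(N − 1)]; chi-square = (a − E)²/V.

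For 16 v 7: m = 23, E = 11.5, V = 625 × 23 × 27 / (2500 × 49) = 3.168, chi-square = 4.5²/3.168 = 6.39, p = 0.011.

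Recoding k dronabinol participants as not improved, placebo assumed at 7/25:

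| k | Dronabinol v placebo | Difference (points) | p |
|---|---|---|---|
| 0 | 16 v 7 | 36 | 0.011 |
| 1 | 15 v 7 | 32 | 0.024 |
| 2 | 14 v 7 | 28 | 0.047 |
| 3 | 13 v 7 | 24 | 0.086 |
| 4 | 12 v 7 | 20 | 0.149 |

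The answer depends on the assumed placebo rate. At 5/25, the p-value first exceeds 0.05 at the fifth recode (11 v 5, p = 0.072). At 10/25, 16 v 10 is not significant even before recoding (p = 0.093). From a start close to the threshold, one recode is enough: 15 v 8 gives chi-square 3.866, p = 0.049, and 14 v 8 gives p = 0.091.

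**5. Chance of a favourable result when the improved-and-tolerated rates are equal**

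Assume the same true rate of improved and tolerated in both arms, between 20% and 40%, plus an extra share of dronabinol participants who stop for intolerance while rated improved. Exact enumeration of two binomials with 25 per arm and a two-sided 0.05 level gives the probability that CMH favours dronabinol:

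- no extra share: about 3%
- 4 points (1 of 25): 5 to 6%
- 8 points (2 of 25): 9 to 10%
- 12 points (3 of 25): 15 to 17%

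**6. Would a test of premature termination help?**

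For 4/25 v 1/25 Fisher's exact test gives p = 0.35. A test has little power at this size; the information lies in the table of counts and reasons.

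**The case against.** The strongest reply is that CGI-I here rates symptoms. Someone whose symptoms improved and who stopped for side effects did improve on that construct, and tolerability is handled separately. Counting stops as non-response answers a different question. This stands. A reader might infer that the carried-forward response rate is simply biased, but that holds only if response is meant to include staying on treatment, and no section says so. The case is for showing both readings, not for declaring the planned one wrong.

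A reader might also infer that such a stop counts as a success and nowhere as a failure. The documents do not support that. The underlying adverse event enters the Fisher comparison, Safety Assessments does commit to evaluating premature termination, and the PI writes a report on decisions about participant disposition. What is missing is narrower: a between-arm summary of the stops.

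Nor does a good week-2 or week-4 rating necessarily survive to endpoint. Anyone who attends the early termination visit is rated again, and that rating becomes the last one. It can still be 1 or 2, and attendance depends on when the participant can come in, so the visit weakens the concern without removing it.

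Finally, CGI-I is a secondary endpoint, although its test is described under Primary endpoint analysis. It also goes into a mixed model without carrying forward, which does not count stopping as failure either. The plan expects few drop-outs. These facts limit how much is at stake.

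**Conclusion.** The point holds as a cheap improvement. The stated rule can count a stop for intolerance as improved at endpoint, no planned analysis shows how far the responder result depends on that, and premature termination has no summary by arm or reason.

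The only size that follows directly from the plan is 4 points per recoded participant at 25 per arm. That one to three such stops could change the result rests on assumed response counts; other placebo rates need five recodes, or start from a non-significant result. The documents give no placebo response rate, no dropout rate and no rate of stopping for intolerance, so whether any such case will occur is unknown.

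**What to change.** In Primary endpoint analysis, add a prespecified CGI-I response analysis in which participants who stop study treatment before week 10 are counted as not improved. If the sponsor prefers to count only stops for adverse effects this way, the plan should say so in advance, because the broader rule also recodes stops unrelated to tolerability. Report it beside the carried-forward version and state which of the two leads.

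Record the reason for every stop. In Safety analyses, add a descriptive table of premature termination by arm and reason.

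Cost: a few sentences, one reason field, one extra response analysis and one table; no added participants or visits. The downside is that response rates in the new analysis can only stay the same or fall. If stops among improved participants are more common on dronabinol, its rate falls further than the placebo rate and the contrast between arms shrinks.
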